# 9.2 Statistical Methods and Properties

The study will be monitored for futility and excessive toxicity in cohorts of 10 as described below. If the trial does not stop early, we will estimate the clinical benefit rate and the response rate separately with appropriate 95% confidence intervals. We will also estimate the progression free survival (PFS) and overall survival (OS) using Kaplan-Meier methods.

#### 9.4 General Statistical Considerations

Tabulations will be produced for appropriate demographic, baseline, efficacy and safety parameters. For categorical variables, summary tabulations of the number and percentage of subjects within each category (with a category for missing data) of the parameter will be presented, as well as two-sided 95% confidence intervals, unless otherwise stated. For continuous variables, the number of subjects, mean, median, standard deviation (SD), minimum,

and maximum values will be presented. Time-to-event data will be summarized using Kaplan-Meier methodology using 25th, 50th (median), and 75th percentiles with associated 2-sided 95% confidence intervals, as well as percentage of censored observations.

No imputation of missing efficacy data is planned. For time-to-event analyses, patients who have no efficacy evaluations for disease recurrence will be considered censored at time 0.

For AEs, missing dates will not be imputed, however, if partial dates are available, they will be used to assess if the AE occurred during the treatment period. Missing severities of AEs will not be imputed and will be considered missing in any tabulations of AE severity. If an AE is missing a response to the question regarding relationship to treatment, the event will be considered to be related.

Evaluations will be performed separately for each trial arm.

# 9.4.1 Demographics and Baseline Characteristics

The demographic characteristics to be summarized will include gender, race, ethnicity (Hispanic origin), and age at time of consent. For gender, race and Hispanic origin, the summary statistics will be the number and percentage of patients within each group or the total sample. The categories for race will be those recorded in the database. For age at time of consent, the mean, median, minimum, maximum, and standard deviation will be provided for each group and the total sample.

Baseline characteristics include: Performance status, duration from initial diagnosis, response to previous therapy (Y/N).

# 9.3 Sample Size Determination

There will be 3-6 patients enrolled per dose level in the dose escalation phase of the combination of M6620 and avelumab.

Each dose expansion arm may have up to 30 patients each. A 3-stage design with 10 patients in each stage will be utilized. We will stop after the 1st stage if we see 0 successes in 10 evaluable patients on RP2D, after the 2nd stage if we see < 2 successes in 20 evaluable patients, and we will declare the treatment worthy of further study if we see > 3 successes in 30 evaluable patients. If we set p0 (highest success rate for unacceptable treatment) = 5% and p1 (lowest success rate for acceptable treatment) = 20%, this design has alpha = 5%, 80% power and probability of early termination under p0 of 60% after 1st stage and 79% after either 1st or 2nd stage.

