### **Exploratory Endpoints**

- 1. Correlation between clinical benefit (CBR, ORR, PFS, or OS) and ATM mutations and/or protein loss.
- 2. Assessment of homologous recombination deficiency (HRD) score and replication stress response defect (RSRD) score.
- 3. Immunohistochemistry, immunofluorescence, and flow cytometry analysis of immune cell subsets and markers, including PD-L1.
- 4. Whole exome sequencing, RNA-sequencing, and Reverse Phase Protein Array (RPPA) analysis of pre-, on-treatment, and optional at-progression tumor biopsies.
- 5. PK summary statistics, concentration-time profiles and parameters (e.g. CL, AUC,  $C_{max}$ ,  $T_{max}$ , half-life if estimable).

Study Considerations	
 
Actionable variant(s) in the following DDR genes, based on next generation sequencing (NGS), will be considered in this trial: ARID1A, ATM, ATR, ATRX, BAP1, BARD1, BRCA1/2, BRIP1, CDK12, CHEK2, FANCA, FANCC, FANCD2, FANCE, FANCF, FANCM, MRE11A, MSH2, NBN (NBS1), PALB2, RAD51, RAD51C, RAD51D, SMARCB1, and VHL. Other appropriate aberrations may be considered for patient selection at the discretion of the PI depending on emerging data.
 
CLIA-approved immunohistochemistry analysis of ATM protein loss may also be considered.
 
Interim analysis of toxicity will be performed in cohorts of 10 patients.
 
Interim analysis for futility will be performed in cohorts of 10 patients.
 

Planned Sample	3-6 patients for dose escalation.
Size	30 patients for dose expansion.
	The accrual may be up to 36 patients

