# Dose Expansion for Arm A

- RP2D
- · Patients with advanced solid tumors harboring DDR defects
- N = 10 up to a maximum of 30 patients\*

\*Note: a 3-stage decision with 10 patients at each stage will be used for each regimen in the dose expansion phase of the trial. We will stop after the 1st stage if we see 0 successes in 10 patients,

after the 2nd stage if we see < 2 successes in 20 patients, and we will declare the treatment worthy of further study if we see > 3 successes in 30 patients.

QW = weekly; Q2W = every two weeks; MTD = Maximum Tolerated Dose; RP2D = Recommended Phase 2 Dose

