#### 6.5 Patient Withdrawal

Patients will be free to discontinue treatment or withdraw from the study at any time, for any reason, or they may be withdrawn/ removed if necessary in order to protect their health (see reasons for withdrawal below). It is understood by all concerned that an excessive rate of withdrawals can render the study uninterpretable; therefore, unnecessary withdrawal of subjects should be avoided. Patients who are withdrawn from the study outside of the DLT period will not be replaced.

Patients will be removed from further treatment for the following reasons:

- a. Confirmed evidence of true disease progression (See Section 5.2.5.4)
- b. Non-compliance
- c. Need for treatment with medications not allowed by the study protocol (unless the medication is temporary and continuation of study treatment following cessation of that medication is reasonable at the discretion of the Investigator and Study Monitor)
- d. Patient no longer consents to participate in the study
- e. Intercurrent illness that interferes with study assessments
- f. Incidence or severity of AEs in this study indicates a potential health hazard to the patient
- g. Investigator's discretion
- h. Pregnancy
- i. Termination of the study

Reasons for withdrawal from study follow up may include:

- a. Completed study follow up
- b. Study terminated by Sponsor
- c. Lost to follow up
- d. Refusal of further follow up for survival
- e. Death

If there is a medical reason for withdrawal of treatment, the patient will remain under the supervision of the investigator until the AEs have been resolved or declined to baseline values.

If a patient has failed to attend scheduled assessments in the study, the investigator must determine the reasons and circumstances as completely and accurately as possible.

In case of premature discontinuation of the study treatment, the investigations scheduled for the EOT and the follow-up visits should be performed, if possible. The reason for discontinuation has

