# 9.1.3 Response Analysis Set

All enrolled patients who receive at least one (1) dose of study medication with baseline assessment and have at least one post-baseline tumor assessment will be considered evaluable for response.

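### The 80% power in Section 9.3 assumes 30 evaluable expansion patients, but expansion stops at 30 patients with no allowance for any who are never scanned after baseline

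*Combined protocol and SAP*

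**What the plan says.** Section 9.3 sets three looks, all in evaluable patients. The first is "We will stop after the 1st stage if we see 0 successes in 10 evaluable patients on RP2D", the second is "after the 2nd stage if we see < 2 successes in 20 evaluable patients", and the final rule is "we will declare the treatment worthy of further study if we see > 3 successes in 30 evaluable patients". It takes p0 = 5% and p1 = 20% and claims alpha 5%, power 80%, and early termination under p0 of 60% after stage 1 and 79% by stage 2.

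Section 9.1.3 defines the denominator: patients with a dose and a baseline assessment who "have at least one post-baseline tumor assessment will be considered evaluable for response". Section 9.5 uses the same population for the efficacy analyses.

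Section 3.2 (Dose Expansion for Arm A) and note 2 to Figure 2 give the same thresholds for 10, 20 and 30 patients, without the word evaluable. The cap is "N = 10 up to a maximum of 30 patients"; the synopsis has "30 patients for dose expansion" and total accrual of up to 36.

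On replacement, Section 6.5 says "Patients who are withdrawn from the study outside of the DLT period will not be replaced". The DLT window is 28 days (Section 3.4). Sections 3.3 and 9.1.2 provide replacement only for patients not evaluable for DLT in dose escalation.

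**The concern.** If 30 is both the most patients expansion may enrol and the number of evaluable patients the final rule needs, the rule runs as specified only when nobody is lost before a first post-baseline scan. The plan does not say what happens otherwise. It gives no threshold for a final count below 30, no allowance for loss, and no imputation of missing efficacy data (Section 9.4).

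Two things are at stake. If the threshold of at least 4 successes is kept with fewer evaluable patients, power falls and the error runs toward dropping an active regimen. Separately, an evaluable-only count removes patients who die or leave early without a scan from the go/no-go decision, although they are treatment failures in any practical sense. Eligibility requires a life expectancy of at least 12 weeks and the first scheduled scan is at week 8, so some loss is plausible, although the documents do not quantify it.

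**Working it through.** **Inputs.** Stage sizes 10, 10, 10; stop at 0 of 10 or at most 1 of 20; success at 4 or more; p0 = 0.05, p1 = 0.20 (all Section 9.3). Cap of 30 in expansion (synopsis, Sections 3.2 and 9.3). The proportion never scanned after baseline is not given, so it is varied below.

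**Formula.** Let N be the final evaluable number, with looks kept at 10 and 20. The probability of declaring success is the single-stage probability less the paths that stop early but would have reached 4:

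P(go) = P[Bin(N,p) ≥ 4] − A·P[Bin(N−10,p) ≥ 4] − B·P[Bin(N−20,p) ≥ 3]

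A = (1−p)^10 is the chance of stopping at look 1. B = 10p(1−p)^9·(1−p)^10 is the chance of exactly 1 success in the first 10 and none in the next 10, which stops at look 2.

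**Reproducing the plan (N = 30).**
- Early termination at p = 0.05: A = 0.5987 and B = 0.1887, sum 0.7874. The plan says 60% and 79%.
- Alpha: 0.0608 − 0.5987 × 0.0159 − 0.1887 × 0.0115 = 0.0608 − 0.0095 − 0.0022 = 0.0491.
- Power at p = 0.20: 0.8773 − 0.1074 × 0.5886 − 0.0288 × 0.3222 = 0.8773 − 0.0632 − 0.0093 = 0.8048.

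All four stated figures are confirmed. The margin above 80% is 0.5 points.

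**Fewer than 30 evaluable, same looks and threshold.**

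| Never scanned | Evaluable N | Alpha | Power |
|---|---|---|---|
| 0 | 30 | 4.9% | 80.5% |
| 1 | 29 | 4.5% | 79.4% |
| 2 | 28 | 4.2% | 78.0% |
| 3 | 27 | 3.8% | 76.5% |
| 6 | 24 | 2.7% | 70.3% |

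For example, at N = 27 power is 0.8177 − 0.0484 − 0.0043 = 0.7650; at N = 24 it is 0.7361 − 0.0324 − 0.0008 = 0.7029.

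**Counting all 30 treated, never-scanned patients as failures.** The success rate per treated patient is p × (1 − d), where d is the assumed proportion never scanned. If 20% is the rate among evaluable patients:
- d = 10%: p = 0.18; power 0.8144 − 0.0684 − 0.0109 = 0.7351.
- d = 20%: p = 0.16; power 0.7295 − 0.0701 − 0.0120 = 0.6474.

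If 20% is defined per treated patient, power stays at 80.5%.

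**Enrolment needed to reach 30 evaluable, 30/(1 − d).** 30/0.9 = 33.3, so 34 at 10% loss; 30/0.8 = 37.5, so 38 at 20%. Both exceed the expansion cap.

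**The case against.** The case against has several parts, and much of it stands.

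- **Missing the week-8 scan does not make a patient non-evaluable.** A reader might infer that it does. Section 9.1.3 accepts any post-baseline assessment. The Study Calendar has imaging at end of treatment, Section 6.3 gives every patient who discontinues that visit, and Section 7.3 calls for an unscheduled scan when progression is suspected. Only patients with no scan at all are lost. This stands and makes the likely loss smaller.
- **Non-replacement before the first scan is not a blanket rule.** Section 6.5 bars replacement only outside the DLT period. For expansion patients lost in days 1–28 the text neither forbids nor provides it. This stands, but the cap leaves no room for a replacement in either case.
- **Other patients might fill the gap.** Section 9.3 speaks of evaluable patients on the RP2D. If escalation patients at that dose counted, up to 36 in total could yield 30 evaluable despite six losses. The documents do not say they count, and the rule is placed in expansion. Section 3.1 also says basket sizes may be increased on pre-defined signals, but Sections 3.2 and 9.6, to which it points, give no rule taking expansion above 30.
- **Treating losses as failures does not raise power.** With 20% per evaluable patient, 73.5% and 64.7% are lower than the 76.5% and 70.3% under the current evaluable count. This is true. The case for the change is a defined denominator that early deaths and drop-outs cannot escape.
- **The rule serves a secondary objective.** The primary endpoints are adverse events and DLTs. The rule nevertheless stops accrual for futility and decides whether the regimen goes forward.

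**Conclusion.** The concern holds in a limited form. The denominator is inconsistent between Section 9.3 and Section 3.2 with the Figure 2 note. The 80% claim rests on an unstated assumption that all 30 expansion patients are scanned after baseline. The calculation itself is correct.

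The size is conditional. One or two never-scanned patients cost at most about 2.5 points (80.5% to 78.0%), which is minor. Three bring power to 76.5% and six to 70.3%, with alpha falling to 3.8% and 2.7%. These figures assume that the looks stay at 10 and 20 evaluable patients and that the final threshold is unchanged. No loss rate is documented, so the plan does not support the stronger inference that the trial will in fact miss its stated power. What it supports is that the power is guaranteed only at zero loss and that the plan is silent on any other case.

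**What to change.** Use one denominator in Section 3.2, the Figure 2 note and Section 9.3: all patients treated at the RP2D in expansion, with those who have no post-baseline scan counted as failures. Then:

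- Align Sections 9.1.3 and 9.5 with this for the decision rule, so that the evaluable-only population does not contradict it.
- Define p0 and p1 per treated patient. The looks at 10, 20 and 30 are then reachable within the cap, and 80.5% power applies to a 20% rate per treated patient.
- If 20% is meant per evaluable patient, restate power as about 74% at an assumed 10% loss and 65% at 20%.
- State whether escalation patients treated at the RP2D count toward 10/20/30.

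The cost is a change of wording and, under the per-evaluable reading, a less favourable stated power. No patients are added. The alternative is to keep the evaluable denominator, allow replacement until 10/20/30 are evaluable, and raise the expansion cap to about 34 at 10% loss or 38 at 20%. That preserves 80% per evaluable patient but costs patients and still leaves early losses out of the decision.

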#### 9.4 General Statistical Considerations

Tabulations will be produced for appropriate demographic, baseline, efficacy and safety parameters. For categorical variables, summary tabulations of the number and percentage of subjects within each category (with a category for missing data) of the parameter will be presented, as well as two-sided 95% confidence intervals, unless otherwise stated. For continuous variables, the number of subjects, mean, median, standard deviation (SD), minimum,

and maximum values will be presented. Time-to-event data will be summarized using Kaplan-Meier methodology using 25th, 50th (median), and 75th percentiles with associated 2-sided 95% confidence intervals, as well as percentage of censored observations.

No imputation of missing efficacy data is planned. For time-to-event analyses, patients who have no efficacy evaluations for disease recurrence will be considered censored at time 0.

For AEs, missing dates will not be imputed, however, if partial dates are available, they will be used to assess if the AE occurred during the treatment period. Missing severities of AEs will not be imputed and will be considered missing in any tabulations of AE severity. If an AE is missing a response to the question regarding relationship to treatment, the event will be considered to be related.

All evaluations will be performed separately for each trial arm.

# 9.4.1 Demographics and Baseline Characteristics

The demographic characteristics to be summarized will include gender, race, ethnicity (Hispanic origin), and age at time of consent. For gender, race and Hispanic origin, the summary statistics will be the number and percentage of patients within each group or the total sample. The categories for race will be those recorded in the database. For age at time of consent, the mean, median, minimum, maximum, and standard deviation will be provided for each group and the total sample.

Baseline characteristics include: Performance status, duration from initial diagnosis, response to previous therapy (Y/N).

# 9.5 Efficacy Analysis

The efficacy population will consist of all patients who receive at least one dose of study medication with baseline assessment and have at least one (1) post-baseline tumor assessment. This population will be used for primary analyses of efficacy.

# 9.5.1 Efficacy Evaluation

Clinical efficacy will be measured by clinical benefit rate (CBR) per RECIST v1.1 and irRECIST. CBR is defined as complete response (CR) + partial response (PR) + stable disease (SD) > 6 months. Overall response rate (ORR) will be measured using RECIST 1.1 criteria. Secondary efficacy endpoints include objective response (CR+PR), progression free survival (PFS), Duration of Response (DoR), overall survival (OS) and ORR. A 95% CI of response rate will be estimated based on the binomial distribution.

### 9.6 Safety Monitoring

The safety population will consist of all patients who have received any amount of study medications. We will employ Thall and Simon methods (1994) to perform interim safety monitoring every 10 patients for up to 30 patients. Formally, denote  $q_T$  as the probability of toxicity and assuming a non-informative beta(0.3,0.7) prior for  $q_T$ , we will stop the study if we determine that

there is more than an 80% chance that the posterior probability of toxicity is more than 30%. Specifically, our interim monitoring rule for toxicity is:  $Pr [q_T > 30\% | data] > 0.8$ . The stopping boundaries corresponding to the above monitoring rule are to terminate study if (# patients with DLT) / (# patients evaluated) >=5/10, 8/20. The calculations were performed using MultcLean Desktop v 2.0.1. We will compare the proportion of patients with CTCAE grade 3 or higher treatment-related toxicities between treatments using chi-squared test or Fisher exact test as appropriate for the data.

Table 7: Expected early stopping probability

True toxicity probability	Early stopping probability	Expected number of patients
		enrolled before stopping
0.2	0.05	29.1
0.3	0.28	25.7
0.4	0.63	19.9
0.5	0.89	14.9
0.6	0.98	11.8

## 9.6.1 Safety Evaluation

Safety analyses will be conducted using the safety population. For the objective of describing the toxicity profile, descriptive statistics will be provided on the grade and type of toxicity by dose level.

#### 9.6.2 Adverse Events

Adverse Events (AEs) will be coded using the NCI CTCAE v5.0 (or MedDRA if code is not available in CTCAE) and displayed separately for patients. Analyses of AEs will be performed for those events that are considered treatment emergent, where treatment-emergent is defined as any AE with onset or worsening of a pre-existing condition on or after the first administration of study medication through 90 days following last dose or any event considered drug-related by the investigator through the end of the study. AEs with partial dates will be assessed using the available date information to determine if treatment-emergent; AEs with completely missing dates will be assumed to be treatment-emergent.

AEs will be summarized by patient incidence rates, therefore, in any tabulation, a patient contributes only once to the count for a given AE preferred term. The number and percentage of patients with any treatment-emergent AE will be summarized separately for patients in the trial. The number and percentage of patients with treatment-emergent AEs assessed by the Investigator as at least possibly related to treatment will also be tabulated. The number and percentage of patients with any grade  $\geq 3$  treatment-emergent AE will be tabulated in the same manner. In the event a patient experiences repeated episodes of the same AE, then the event with the highest severity and/or strongest causal relationship to study treatment will be used for purposes of tabulations.

Serious AEs will also be tabulated. No formal hypothesis-testing analysis of AE incidence rates will be performed. All AEs (treatment emergent and post-treatment) will be listed in patient data listings. By-patient listings will be provided for the following: patient deaths; serious AEs; and AEs leading to withdrawal.

# 9.6.3 Laboratory Data

The actual value and change from baseline to each on study evaluation will be summarized for each clinical laboratory parameter, including hematology and clinical chemistry, separately for all study patients. In the event of repeat values, the last non-missing value per study day/time will be used.

Severity of select clinical lab measures will be determined using CTCAE criteria (e.g. those measures that have a corresponding CTCAE grade classification). Labs with CTCAE grades greater than or equal to 3 will be presented in a data listing. Shift tables that present changes from baseline to worst on-study values relative to CTCAE classification ranges will be produced.

# 9.6.4 Vital Signs and Physical Examinations

The actual value and change from baseline to each on study evaluation will be summarized for vital signs for all study patients combined. By-patient listings of vital sign measurements will be presented in data listings.

Physical examination results at screening will be summarized; all other abnormal physical examination data were to be recorded on the AE eCRF. All examination findings will be presented in a data listing.

#### 9.6.5 Concomitant Medications

The use of concomitant medications will be included in by-patient data listings.

# 9.7 Pharmacokinetic Analysis

Pharmacokinetic analyses for avelumab and M6620 will consist of summary statistics and plots of concentration-time data. Additionally the pharmacokinetic data may be utilized in a population pharmacokinetic analysis to determine typical and individual PK parameters (e.g. CL,  $V_{ss}$ , AUC,  $C_{max}$ ,  $T_{max}$ , half-life if estimable).

#### 9.8 Biomarker Analysis

Biomarker studies outlined in Section 7.5 will be mostly exploratory in nature and considered hypothesis-generating. Statistical methods employed will depend on the extent and nature of the data obtained.

